Insurance and indemnity for clinical study participants and study staff is covered within the NHS Indemnity Arrangements for clinical negligence claims in the NHS, issued under cover of HSG (96)48. There are no special compensation arrangements, but study participants may have recourse through the NHS complaints procedures.

The University of Nottingham as research Sponsor indemnifies its staff with both public liability insurance and clinical trials insurance in respect of claims made by research subjects.

STUDY CONDUCT

Study conduct may be subject to systems audit for inclusion of essential documents; permissions to conduct the study; CVs of study staff and training received; local document control procedures; consent procedures and recruitment logs; adherence to procedures defined in the protocol (e.g. inclusion / exclusion criteria, timeliness of visits); accountability of study materials and equipment calibration logs.

The Study Coordinator/Academic Supervisor, or where required, a nominated designee of the Sponsor, shall carry out a site systems audit at least yearly and an audit report shall be made.

STUDY DATA

Monitoring of study data shall include confirmation of informed consent; source data verification; data storage and data transfer procedures; local quality control checks and procedures, back-up and disaster recovery of any local databases and validation of data manipulation. The Study Coordinator/Academic Supervisor,, or where required, a nominated designee of the Sponsor, shall carry out monitoring of study data as an ongoing activity.

Entries on CRFs will be verified by inspection against the source data. A sample of CRFs (10% or as per the study risk assessment) will be checked on a regular basis for verification of all entries made. In addition the subsequent capture of the data on the study database will be checked. Where corrections are required these will carry a full audit trail and justification.

Study data and evidence of monitoring and systems audits will be made available for inspection by the REC as required.

RECORD RETENTION AND ARCHIVING

In compliance with the ICH/GCP guidelines, regulations and in accordance with the University of Nottingham Code of Research Conduct and Research Ethics, the Chief or local Principal Investigator will maintain all records and documents regarding the conduct of the study. These will be retained for at least 7 years or for longer if required. If the responsible investigator is no longer able to maintain the study records, a second person will be nominated to take over this responsibility.

The study documents held by the Chief Investigator (CI) on behalf of the Sponsor shall be finally archived at secure archive facilities at the University of Nottingham. This archive shall include all anonymised audio recordings, study databases and associated meta-data encryption codes.

DISCONTINUATION OF THE STUDY BY THE SPONSOR

The Sponsor reserves the right to discontinue this study at any time for failure to meet expected enrolment goals, for safety or any other administrative reasons. The Sponsor shall take advice as appropriate in making this decision.

STATEMENT OF CONFIDENTIALITY

Individual participant medical or personal information obtained as a result of this study are considered confidential and disclosure to third parties is prohibited with the exceptions noted above.

Participant confidentiality will be further ensured by utilising identification code numbers to correspond to treatment data in the computer files.

Such medical information may be given to the participant's medical team and all appropriate medical personnel responsible for the participant's welfare.

If information is disclosed during the study that could pose a risk of harm to the participant or others, the researcher will discuss this with the CI and where appropriate report accordingly.

Data generated as a result of this study will be available for inspection on request by the participating physicians, the University of Nottingham representatives, the REC, local R&D Departments and the regulatory authorities.

PUBLICATION AND DISSEMINATION POLICY

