FULL TITLE OF THE CLINICAL STUDY

What is the clinical experience of maintaining patient safety in hospital in patients with temporary or permanent loss of cognitive function? A Mixed Methods Study

Protocol Final Version 1.0 06.11.2024
(Last updated 11.05.2026)

Short title: Clinical Experience of Maintaining Patient Safety in Hospital

Acronym: CEMPSIH

IRAS Project ID: 347285

Study Sponsor: University of Nottingham

Sponsor reference: **24065**

Funding Source: This study is part of a PhD study funded by a scholarship awarded by the Engineering and Physical Sciences Research Council (EPSRC).

STUDY PERSONNEL AND CONTACT DETAILS

Sponsor: Contact name	University of Nottingham [name] Head of Research Integrity, Governance & Compliance University of Nottingham [name] [contact]
Chief investigator:	Asst. [name] Associate [name] Human Factors Research Group Faculty of Engineering University of Nottingham Phone: Email: [contact]
Co-investigators:	
[name] [name] Principal Research Fellow, NIHR MindTech Research Centre Institute of Mental Health Email: [contact]
 
[name] Principle Research Fellow Centre for Rehabilitation and Ageing Research School of Medicine, Queens Medical Centre Email: [contact]
 
[name] Student ID: [name] Human Factors Research Group [contact] Email: [contact]

Study Coordinating Centre:	Human Factors Research Group Faculty of Engineering, University of Nottingham, [name]

SYNOPSIS

Title	What is the clinical experience of maintaining patient safety in hospital in patients with temporary or permanent loss of cognitive function? A Mixed Methods Study
Short title	Clinical Experience of Maintaining Patient Safety in Hospital (CEMPSIH)
Chief Investigator	Associate [name]
Objectives	To test whether there is a universal professional experience of maintaining patient safety in hospitals, with patients who have impaired cognitive function
Study Configuration	Mixed Methods, Multi-centre, Exploratory Sequential Strategy
Setting	Secondary care - Acute Hospital Trusts
Number of participants	128 participants overall. Up to 32 participants per Hospital (16 Nursing staff, 8 Therapists and 8 Medical Doctor or associates)
Eligibility criteria	Direct patient facing healthcare workforce responsible for managing and preventing accidental falls in the NHS.

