- To disprove the null hypothesis that “there is no universal clinical experience of accidental fall prevention in hospitals with patients who have impaired cognitive function”.

SECONDARY OBJECTIVES

[figure not shown]
- To inductively generate a questionnaire to be distributed to healthcare professionals and care workers in a future study.
- To gather an evidence base for the co-created design and testing of fall prevention interventions as part of the longer term PhD project

The investigator has completed the HRA tools which have confirmed the study is classed as research and that it does not require NHS REC review. The investigator has also successfully undertaken the Good Clinical Practice training to provide public assurance that the rights, safety and wellbeing of research participants are protected and that research data are reliable.

STUDY DESIGN

STUDY CONFIGURATION

This is a multi-centre qualitative study utilising a purposive sampling strategy. Healthcare workers directly involved in preventing falls in hospital will be invited to contribute to the study via an email from their ward manager or clinical lead. Participants will be asked to respond directly to the researcher to indicate their interest in the study. They will be selected to ensure Medical and Surgical wards are represented to ensure generalisability of outcomes. Overall aim will be for up to 16 participants from the nursing team, registered and unregistered, up to 8 therapist participants and up to 8 doctors (*Figure 1- Participant Study Flowchart*).

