 17. Investigator will share themed analysis for comment. Method to suit participant such as Teams meeting, email, face to face or phone call.
 18. Investigator will bring together themes from all simulations and focus groups and synthesise any generalised views ensuring anonymity.

Compliance

Non-attendance of any staff member will be followed up with a phone call to number acquired during the consent process (their preferred form of communication). Participants will be offered the opportunity of an alternative date where available.

There is some contingency built into each simulation and focus group to allow for 2 participants not to turn up to their simulation. The focus group will be made up from 2 simulation groups and therefore should be a group of up to 8 for the discussion. Group numbers below 4 or with any profession not represented will not be considered quorate. In this event the investigator will attempt to organise an additional session for consented people who were unable to attend.

Criteria for terminating the study

In the unlikely event that the study is to be terminated on one or all sites the research data will be archived.

ANALYSES

Methods

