The focus group will be recorded, transcribed and analysed using Nvivo 14 (a software application to assist with coding) assigning meanings through essence capturing (Saldaña, 2021) by creating codes. These codes will be generated for the purpose of pattern detection to interpret data and deduct meaning (Vogt et al., 2012). This can be interpreted as imposing values or as reductionist but using constructivist principles will allow valuing multiple perspectives and will establish a deeper understanding of staff experience (Creswell, 2018). It is difficult to completely remove the investigator's values when analysis is done, but by sharing the analysis with the participants and the research team there is transparency and reflexivity, recognising the 'importance of self' (Humphries, 2003). The analyses will be discussed with the participants so any disagreement will also be recorded for the reader to consider. The primary intent of the qualitative phase is to design a measure that is grounded in issues raised by patient facing staff and PPI representatives rather than individual opinion or experience.

Sample size and justification

The investigator is seeking to involve a small number of relevant direct patient facing healthcare workers to provide in depth information about the lived experience of preventing and managing in-patient falls. By purposefully involving participants who are charged with preventing in-patient falls as part of their usual practice the investigator will be able to collect in depth knowledge of the experience and associated heuristics. 8 simulations and focus groups in 4 different hospitals on different geographical sites are planned generating 16 datasets. The investigator will continue until repeated themes suggests there is a degree of homogeneity in experiences or not (Creswell, 2018). This is with the intention of adopting a phenomenological approach but depending on the data arising sampling could continue to allow grounded theory to inform the questionnaire (Creswell, 2023). The final sample size will

not be determined until a sufficient database has been collected to develop the content of the questionnaire for a future study.

ADVERSE EVENTS

The occurrence of an adverse event as a result of participation within this study is not expected and no adverse event data will be collected.

ETHICAL AND REGULATORY ASPECTS

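### The primary objective promises a verdict on universality that a purposive qualitative study of up to 16 focus groups in up to 4 hospitals cannot give

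*Combined protocol and SAP*

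**What the plan says.** - **Objective.** Under Primary objective the aim is "To disprove the null hypothesis that" "there is no universal clinical experience of accidental fall prevention in hospitals with patients who have impaired cognitive function". The synopsis puts it neutrally: "To test whether there is a universal professional experience of maintaining patient safety in hospitals, with patients who have impaired cognitive function".
- **Design and sampling.** Study configuration states: "This is a multi-centre qualitative study utilising a purposive sampling strategy". On ward types it adds: "They will be selected to ensure Medical and Surgical wards are represented to ensure generalisability of outcomes". Under Recruitment, staff volunteer by contacting the investigator themselves.
- **Size.** The schedule in Figure 2 and the Study Duration text give maxima: 32 simulations, 16 focus groups and 128 participants across 4 hospitals.
- **Analysis.** Under Analyses, Methods, the focus groups are transcribed and coded in NVivo 14 on constructivist principles. The analysis is shared with participants, and their disagreements are recorded. The same section says: "The primary intent of the qualitative phase is to design a measure that is grounded in issues raised by patient facing staff". Secondary objectives, by contrast, is where the questionnaire is listed, for use in a future study.
- **When to stop.** Sample size and justification lets sampling run until recurring themes point to some homogeneity of experience, or to its absence. The final number stays open until there is enough material for the questionnaire.
- **Synthesis.** Step 18 of the Study regimen reads: "Investigator will bring together themes from all simulations and focus groups and synthesise any generalised views ensuring anonymity".

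**The concern.** The primary objective decides what the study will be said to have shown. Here it is worded as the rejection of a null hypothesis, yet nothing later in the protocol could produce that result. There is no outcome variable, no definition of universal, no threshold and no test. A statement at the end that the null was, or was not, disproved would have no stated basis.

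The direction of the null makes this worse. Rejecting a claim that no universal experience exists means affirming a universal. That is the one kind of statement that a limited set of volunteers cannot confirm, however strongly they agree.

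The protocol also gives two different primary aims: the hypothesis under Study objectives and purpose, and the design of a measure under Analyses. The sampling rule serves both, without saying which governs.

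**Working it through.** **1. Reproduce the plan's counts.** From Figure 2: 4 hospitals, 2 days each, 4 simulations a day, 4 participants per simulation, 2 focus groups a day.
- Simulations: 4 × 2 × 4 = 32.
- Participants: 32 × 4 = 128.
- Focus groups: 4 × 2 × 2 = 16.

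All three match the stated maxima. The documents give no alpha, power, effect measure or margin, so there is no power calculation to reproduce.

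**2. Look for a rule that could reject the null.** The nearest is the stopping rule under Sample size and justification. It refers to some degree of homogeneity, with no threshold. It tells the investigator when to stop sampling; it does not say what finding would count as universal. Some homogeneity is also a weaker claim than universality.

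**3. Illustrate what complete agreement could show.** Assume, more favourably than the protocol allows, that units are a random independent sample and that a theme is simply present or absent. If it is present in all n units, the exact one-sided 95% lower bound for the share of units that have it is 0.05^(1/n).
- Focus group as unit, n = 16: 0.05^(1/16) = 0.829. Up to about 17% of such groups could lack the theme.
- Hospital as unit, n = 4: 0.05^(1/4) = 0.473. Up to about 53% of hospitals could lack it.

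**4. Allow for groups nested in hospitals.** With 4 groups per hospital, the effective number is 16 / (1 + 3 × ICC) and the bound is 0.05^(1/effective number). The documents give no intracluster correlation (ICC), so a range is assumed.

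| Assumed ICC | Effective n | Lower bound |
|---|---|---|
| 0 | 16.0 | 82.9% |
| 0.1 | 12.3 | 78.4% |
| 0.3 | 8.4 | 70.1% |
| 0.5 | 6.4 | 62.6% |
| 1 | 4.0 | 47.3% |

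**5. Chance of missing a real minority.** If 10% of groups truly differed, all 16 would still agree with probability 0.90^16 = 0.185. If 5% differed, the probability is 0.95^16 = 0.44.

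**6. Set the two primary aims side by side.** The Analyses wording is limited to the qualitative phase. That phase is the whole of this study, since the questionnaire is to be distributed in a future one. The limitation therefore does not remove the conflict with the listing of the questionnaire as secondary.

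**7. Set the feedback passages side by side.**
- The synopsis puts the 30-minute feedback session at completion of the study.
- Study Duration refers to collective theming and then to presenting the analysis back to participants.
- Participant Duration puts follow-up within 2 months of the session, and Expected duration gives 3 months in all.
- Steps 15 and 17 describe checking the themes of the discussion, and both come before the cross-site synthesis in step 18.

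These passages do not settle which analysis participants see.

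**The case against.** The strongest reply is that this is exploratory constructivist work and should not be held to the standards of a test. Much of that stands. The protocol values multiple perspectives, undertakes to record disagreement, and in step 18 speaks only of whatever general views emerge. Its stopping rule allows for a negative answer. The stated purpose (barriers to preventing falls and what staff believe works) and the questionnaire work remain achievable. The sample numbers are maxima, and the final size is deliberately open. None of this rescues the objective, because these are reasons for not framing it as a null hypothesis.

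A reader might go further than the documents allow in three ways.
- **That the mixed-methods label is false.** The synopsis declares an exploratory sequential strategy, in which a later quantitative phase is expected. The label is not the defect.
- **That participants never check the cross-site view.** The step order suggests this, but the synopsis and Study Duration can be read as feedback after collective theming. The timing is inconsistent; the check is not shown to be absent.
- **That recurring themes will be reported as proof.** The protocol does not say so. The wording leaves room for it, and that is as far as the text goes.

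**Conclusion.** The concern holds and the objective's wording must be corrected. As written, it asks for rejection of a null that this design cannot reject. This rests on the text alone: purposive self-selected sampling, thematic analysis, no definition of universal and no decision rule.

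The 83% and 47% bounds are illustrations, not properties of the study. They assume random, independent units and a yes/no theme, none of which the protocol provides. They are probably generous, because volunteers are not a random sample and every group discusses the same kind of simulated fall, which builds in some common ground.

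A reader might infer that the study can conclude nothing. That is too strong. It can describe shared and divergent experience, a clear counter-example could count against universality, and it can supply questionnaire content. What it cannot do is conclude that a universal experience exists, or claim that including medical and surgical wards secures generalisability.

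**What to change.** 1. Replace the primary objective, and the synopsis objective with it, by a descriptive one: to describe which experiences of preventing falls in patients with impaired cognition are shared across professions and hospitals, which differ between them, and what questionnaire content follows. This also removes the conflict with the Analyses section.
2. Move any test of universality to the future questionnaire study, with a defined measure and threshold.
3. In Study configuration, claim that the ward mix supports transferability, not that it ensures generalisability.
4. Declare the change as an amendment, and state whether analysis had begun when it was made.
5. Reconcile the feedback timing across the synopsis, the duration sections and steps 15, 17 and 18, so that it is clear whether participants see session themes or the cross-site synthesis.

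Optional: a theme-by-focus-group table showing where each theme is present, absent or contradicted. It must be reported so that nobody can be identified. There are at most 8 doctors and 8 therapists per hospital and participants may know each other, so a breakdown by profession within hospital would strain the anonymity that step 18 requires.

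The cost is wording, plus one table if wanted. Items 1 to 4 leave sampling, simulations and focus groups unchanged. The real downside is a less ambitious headline claim. If item 5 is settled in favour of showing the cross-site synthesis, early sites may exceed the 2-month and 3-month limits, which would then need revising too.
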